5.3 Implementation Outcome Measures

All treatment sessions (across groups A, B and C) will be video recorded. Implementation will be measured by coding twenty-five percent of sessions by 2 Independent Coders (IC's). IC's will be Master's level research staff members or advanced doctoral students in Psychology who have been trained to a reliable standard. Coder reliability will be checked quarterly. Kappa coefficients will be computed; a minimum of .85 will be required for each code. Retraining will be conducted should rater agreement fall below .85. For the qualitative content analysis. Coding differences of within 1 point between the 2 ICs will be considered an agreement. We will report the average score between the two ICs. If the difference is greater than 1 point, a third IC will independently rate the session and the average of the three ICs will be reported. The IC's will code the videos using the measures below (and attached to section 12 of the eIRB application):

 Content fidelity (how well therapists delivered the content as originally intended by the treatment developers), which is our main fidelity measure, will be assessed using the Content Fidelity Checklist (CFC). The CFC will reflect each activity component of the session agenda or outline of the original and adapted treatment protocols. Raters will use a yes-no response scale to indicate whether or not an STS therapist covered a particular component.

 Process fidelity (delivering treatment content while actively engaging clients in therapy and doing it with a sense of competence) will be measured using an instrument based on a 12-item measure developed by John Lochman and colleagues (e.g., Counselor stops to clarify material; counselor's tone is warm and positive; stimulated discussion; stopped to clarify material) rated on a 5-point scale ranging from "not at all" to "very often." We will use the total score (Overall Process Fidelity). This measure has excellent internal psychometric properties.

Each supervision/consultation session will also be audio/video-recorded. After each session, supervisors will complete the Supervision Rating Scale (SRS) and the consultants (TT+) will complete the Consultation Rating Scale (CRS). Our team developed both measures. The SRS and CRS measure supervision/consultation content and process as detailed in the training manual (e.g., preparing for next session; Demonstrated empathy and provided positive reinforcement).

The supervisions/consultation sessions will also be coded for interruptions and session length. Service interruption is defined as the degree to which therapists are fully available for supervision and treatment sessions. We will derive three scores averaged over the total number of sessions: a) Projected length of the session in minutes minus time spent on interruptions (e.g., answering a phone call, talking about unrelated topics); b) Number of interruptions; c) Total number of supervision / consultation and treatment sessions per group.

To measure differences between support strategies (TT vs. TT+), agency supervisors (12) and therapists (60) in all groups, including participants who did not complete a treatment group but were consented and trained to participate, will be interviewed regarding their perception of the appropriateness and acceptability of the support they receive. A study staff member will conduct open-ended, semi-structured interviews about the process, feasibility and acceptability of the type of support they receive. Interviewers will follow a script to ask questions of supervisors and therapists (e.g., "How acceptable is the level of support you received for the implementation of the FRIENDS protocol?"; "Was the supervision you received from your agency's supervisor appropriate for running groups with children?"; "Was the consultation you received from the research team appropriate for preparing you to conduct supervision with STS therapists?") These interviews will be conducted at the end of each academic year, or once the treatment groups have completed. Qualitative methods will be used because there are currently no psychometrically validated measures that address these areas.

To evaluate potential mediators and moderators of type of support on implementation fidelity, we will use the Index of Inter-professional Team Collaboration for Expanded School Mental Health (IITC-ESMH). The IITC-ESMH is a 26-item measure rated on a 5-point Likert-type scale (1=never to 5=always) designed to measure four organizational constructs: Reflection on Process; Professional Flexibility; Newly Created Professional Activities; Role Interdependence. The measure has excellent psychometric properties. We will use the Total Score in mediator analyses. All school staff members who participate in referring students to the STS programs will be invited to participate in the completion of this measure. For those school staff members who are not study participants, an information

sheet will be provided to them explaining their participation in the completion of this measure.

An additional measure of mediator and moderators of type of support will include a measure of intention, specifically therapists' intention to conduct treatment sessions and participate in supervision. These data will be used to 1) test for differences between the conditions. This is an important secondary outcome because high intentions to use specific evidence based practices are necessary but not sufficient for therapists do use evidence-based practices. These data will also 2) explain why child outcomes do (or don't) differ: Intentions of therapist \rightarrow therapist behavior \rightarrow child outcomes. We will measure therapists' intentions for each condition after training, and two more times during treatment.

6 STATISTICAL CONSIDERATIONS

Variables pertinent to the study aims will be examined for skewed distributions and/or not meeting the assumptions of normality. For such variables, an appropriate method for variable transformation will be selected and applied to stabilize outcomes and their variances and to approximate the normal distribution. The geometric mean, the log transformation and the Box-Cox transformation are examples of such functions. In addition, we will consider non-parametric tests such as the Mann-Whitney test for comparing pre/post changes between two independent groups. Continuous variables will be summarized and described using means, medians, ranges, and standard deviation. Categorical data will be presented by frequencies and percentages. All summaries will be presented by pre and post intervention and by groups. Since randomization was done at the school level, the potential for imbalances at pre-measurements between students who will be part of FRIENDS or CATS groups are anticipated. We will first determine whether student's related demographics, diagnostic, mental health, academic functioning, and therapists' level of experience are balanced in both conditions. We will account for any differences in the analysis by including such variables as covariates.

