4.2 Intervention Implementation (For Students)

Families (students and caregivers) who consent to participate in this intervention, will be enrolled in one of two programs (FRIENDS or CATS, depending on their school's randomization), over the course of several weeks. The students will participate in the program during lunch or a non-academic period during the school day. The programs will be implemented by the student's school-based STS Therapist. Refer to section 1.2.1 for a description of the programs.

Hectic periods of the year when student absenteeism and class trips are more common (1st and 4m Quarters) as well as several class breaks, including winter holidays (approximately 10 days), snow days, Spring Break (1 week) and state mandatory testing of students (2 weeks) will interrupt group sessions. We plan for the interventions to take place primarily during the 2nd and 3rd quarters to eliminate major interruptions in the 1st and 4th quarters. We acknowledge that interruptions might affect the interventions differently, partly because one of the interventions is longer than the other (8 vs. 12 sessions). We were not able to locate a measure that would capture these factors. However, differences in length will be analyzed by adding up the number of days dedicated to instruction for each school when groups are held and divide it by 5. We will then add up the weekly average for each subsequent week and divide it by 8 (CATS) or 12 (FRIENDS). This will give us an index of instruction time for each treatment, which we will then compare and use in covariate analysis.

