6.1 Primary Endpoint

Effectiveness between treatment groups (FRIENDS and CATS) will be tested by calculating the 95% confidence limits (the width of the limit =|4.20|) for the differences in symptom severity, impairment, and academic competence (child outcomes) from pre to post between children receiving FRIENDS and children receiving CATS. If the calculated differences are within the 95% limit, then we will conclude that the two interventions have an equal impact or effect on child outcomes. If any of the differences in child outcomes is/are larger than the upper limit, then we will conclude that one intervention is better than the other. The limit of |4.20| was chosen based on the distribution of the reported mean effect sizes associate with FRIENDS.

Qualitative interviews with supervisors and therapists (perceived acceptability of support strategies) will be audio-recorded, transcribed and entered into NVivo 10.0 for coding and analysis. For each interview, a codebook (of common themes related to the appropriateness and acceptability of the support they received) will be developed and trialed by three coders based on an initial reading of the transcripts, and revised through discussions and subsequent transcript reviews. Coders will meet regularly to compare coding and revise the codebook. This will yield a stable set of qualitative codes that will be used to code the transcripts. Two independent coders will then code all of the transcripts. This iterative process will be continued until consensus is reached and saturation occurs. Coder reliability will be checked quarterly using the inter-rater reliability function in NVivo.

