6.3 Sample Size and Power

Number of students and statistical power. It is anticipated that a total of 284 (142 students per treatment protocol) will complete the proposed study. The published reported effect size of FRIENDS has been estimated to equal 0.56 (cohen's *d*). In testing for equivalence of FRIENDS and CATS, using two one-sided tests with sample sizes of 142 in FRIENDS and 142 in CATS achieves 88% power at a 5% significance level when the true difference between the means is 0 (null hypothesis), the standard deviation of the differences in means is assumed to be 11, and the equivalence limits are -4.20 and 4.20.

Number of therapist and statistical power. To compare TT to TT+ for the implementation of CATS (H2a), with 30 therapists in TT and 30 in TT+ achieve 86% power to detect a

difference of 8% between the null hypothesis that both group means are 80% (content fidelity) and the alternative hypothesis that the mean of group TT is 80% with estimated group standard deviations of 10 and 10 (an estimated effect size=.8) and with a significance level (alpha) of 0.05 using a two-sided two-sample t-test. Similarly, group sample sizes of 30 and 30 achieve 84% power to detect a difference of 0.7 in process fidelity between the null hypothesis that both group means are 4 and the alternative hypothesis that the mean of group TT+ is 4.7 with estimated groups standard deviations of 0.9 and 0.9 (an estimated ES= .78) and with a significance level (alpha) of 0.05 using a two-sided two-sample t-test.

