8 STUDY ADMINISTRATION

8.1 Treatment Assignment Methods

8.1.1 Randomization

Selection and Randomization of schools, therapists and supervisors to intervention conditions:

At least thirty-six schools (potentially up to 41) from mental health agencies will participate in this study. Computerized randomization lists will be generated with random assignment of schools (and therefore, the schools' therapists and supervisors of the agencies participating in this study) to Condition A (FRIENDS/TT), B (CATS/TT), or C (CATS/TT+) with the goal of exposing all agencies to each of the three conditions over the course of the study.

Schools will be stratified according to their size (greater than 625 students (yes/no)). Therefore, a list of 18 schools (including their therapists) will be randomly assigned to the treatment groups and will participate in year 1 of the study (Randomize 1). Schools listed in Randomize 1 will also be used in year 2 while recruiting new therapists and their supervisors (potentially repeat supervisors). We expect this to add 6 new therapists (and their supervisors), per intervention condition, to the study. Schools spanning elementary and middle school grades will run interventions with middle school grades in year 1 and elementary grades in year 2.

From the remaining 18 schools (not randomized yet), a stratified new randomization list will be generated for year two and to be used again in year four (Randomize 2) of the study. As a result, a group of six new therapists and their supervisors (potentially repeat supervisors) per intervention will be recruited for year 3 and a new group of six therapists and their supervisors will be recruited for year 4. Schools spanning elementary and middle school grades will run interventions with middle school grades in year 3 and elementary grades in year 4.

For the 5th year, from the original list of 36 schools using the same stratified randomization method, a new randomization list of schools (Randomize 3) will be generated to recruit a new group of 18 therapists and their supervisors (6 per treatment group). Therefore, a new group of 18 therapists per year (a total of 90 therapists) will participate in this study. Each therapist will participate only one time in this study. In schools spanning elementary and middle school grades, the study conditions will be evenly distributed across grade levels.

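### Schools are randomised and children are treated in small groups, but the FRIENDS–CATS equivalence analysis has no clustering term and its 88% power makes no stated allowance for clustering

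*Combined protocol and SAP*

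**What the plan says.** Section 8.1.1 makes the school the randomised unit: "Computerized randomization lists will be generated with random assignment of schools", with therapists and supervisors following their school. Section 4.2 says families receive "FRIENDS or CATS, depending on their school's randomization". Section 3.2.2 expects each therapist to run a group of 4-6 students. The Abstract and section 3.1 describe therapists as the ones assigned at random.

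Schools are reused. Under 8.1.1, "Schools listed in Randomize 1 will also be used in year 2 while recruiting new therapists and their supervisors". Schools that span both levels "will run interventions with middle school grades in year 1 and elementary grades in year 2". The second list is likewise used for two years, and year 5 is drawn afresh from the same 36 schools.

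Section 6 treats school-level randomisation as a source of baseline imbalance ("Since randomization was done at the school level, the potential for imbalances at pre-measurements") and answers it with covariates: "We will account for any differences in the analysis by including such variables as covariates". Section 6.1 tests effectiveness by "calculating the 95% confidence limits (the width of the limit =|4.20" in absolute value) on pre-to-post differences between children. Section 6.3 says "using two one-sided tests with sample sizes of 142 in FRIENDS and 142 in CATS achieves 88% power", at 5% significance, with SD 11, limits of ±4.20 and a true difference of 0. Neither section gives an ICC, a design effect, a number of clusters or a method for correlated outcomes. The GLM and bootstrap in 6.2 are for costs and name no cluster level.

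**The concern.** Covariates deal with measured differences between arms. They do not in general correct a standard error that treats children from the same school and group as independent. If the ICC is positive, that standard error is too small and the interval too narrow.

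In an equivalence trial this favours the claim under test, because a narrow interval fits inside ±4.20 more easily. When the true difference sits at the margin, CATS would be declared equal to FRIENDS more often than the nominal level allows. Conversely, an analysis that adjusts correctly has less than the stated power, so an inconclusive result is more likely than planned. This comparison is one of the two primary objectives.

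**Working it through.** **Reproducing the 88%.** Inputs from 6.3: 142 per arm, SD 11, margin 4.20, true difference 0, 5% per one-sided test.

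- SE = 11 × √(2/142) = 1.305, and 4.20/1.305 = 3.217.
- Normal approximation: 2Φ(3.217 − 1.645) − 1 = 88.4%. The exact t version on 282 df gives 88.2%.

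The stated figure is therefore the one for a design effect (DE) of 1. With the 95% limits of 6.1, read as requiring the interval to lie within ±4.20, each test is at 2.5% and exact power is 78.7% before any clustering.

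**Cluster structure per arm (8.1.1).** Three lists supply 6 schools each, making 18 school allocations. Twelve serve two years and six serve year 5 only, so there are 12 × 2 + 6 = 30 groups, and 142/30 = 4.73 children per group.

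**Design effect.** Let r be the within-group ICC and k the share of it that persists between the two years of one school allocation:

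DE = 1 + [30 × 4.73 × 3.73 × r + 24 × 4.73² × k × r] / 142

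Adjusted power replaces SE by 11 × √(2 × DE/142), with 2 × 18 − 2 = 34 df. Unadjusted one-sided error at the margin is P(Z > z/√DE), with z = 1.645 or 1.96. The values of r (0.02 / 0.05 / 0.10) are assumptions.

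| | k = 0 (group only) | k = 0.5 | k = 1 (full) |
|---|---|---|---|
| DE | 1.075 / 1.187 / 1.373 | 1.113 / 1.281 / 1.563 | 1.150 / 1.376 / 1.752 |
| Power, 5% tests | 83.7 / 78.8 / 70.4% | 82.1 / 74.6 / 62.0% | 80.4 / 70.3 / 53.9% |
| Power, 2.5% tests | 70.8 / 63.7 / 52.1% | 68.4 / 57.7 / 41.2% | 66.0 / 51.9 / 31.6% |
| Unadjusted error, nominal 5% | 5.6 / 6.6 / 8.0% | 5.9 / 7.3 / 9.4% | 6.3 / 8.0 / 10.7% |
| Unadjusted error, nominal 2.5% | 2.9 / 3.6 / 4.7% | 3.2 / 4.2 / 5.9% | 3.4 / 4.7 / 6.9% |

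Part of the power loss comes from moving to 34 df. With DE = 1 on 34 df, power is 86.8% (5%) and 75.6% (2.5%). Group-only clustering could be given 2 × 30 − 2 = 58 df, which yields 84.5 / 79.7 / 71.5% at the 5% level and 72.5 / 65.5 / 54.1% at the 2.5% level.

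**Thresholds.** At 5 children per group and 282 df, power stays at 86% up to an ICC of about 0.014. With 95% limits, unadjusted error passes 5% only above an ICC of 0.112 (k = 0), 0.075 (k = 0.5) or 0.056 (k = 1).

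**Year-5 redraw.** The three-list scheme was simulated (12,000 runs per setting, stratification ignored, Monte Carlo SE about 0.2 points). The FRIENDS and CATS/TT arms covered about 28 distinct schools, and about 4 appeared in both arms. The unadjusted 5% test ran at 5.2% with no clustering and at 5.4-6.6 / 6.7-8.5 / 8.4-10.6% at the three ICCs. Cluster-robust errors by school-by-list or by school held it at 4.8-5.2%.

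**TT versus TT+.** With independent therapists, the t-test powers reproduce (86.1% content, 84.2% process). Clustering by school (size-weighted 1.8 therapists per school, 34 df) gives 83.9% / 81.8% at ICC 0.05 and 79.8% / 77.6% at 0.20. That loss is small.

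**The case against.** The strongest reply is that the 95% limits in 6.1 are stricter than the 5% tests in 6.3. With 95% limits, unadjusted error stays at or below 4.7% for ICCs of 0.02 and 0.05 in every scenario. That is correct. It still exceeds the 2.5% those limits imply, and power is then under 79% before clustering.

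The error rates also rest on reading 6.1 as interval inclusion. Taken literally, 6.1 compares the observed difference with 4.20. No standard error would then enter the decision, error at the margin would be about 50%, and clustering would not change that. Such a rule would not match the two one-sided tests in 6.3, so interval inclusion is the sensible reading.

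Full correlation across years (k = 1) is an upper bound, since the second year brings new therapists and, in schools spanning both levels, different grades. The group-only and k = 0.5 columns are the more plausible range. At an ICC of 0.02 with group-only clustering, the simulated 5.4% cannot be told apart from the 5.2% seen without clustering.

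The unit conflict is partly resolved by 8.1.1, which says therapists follow their school; clustering arises either way. Separately, 360 students over three arms is 120 per arm, not 142, and at 120 independent-data power is 80.8%. That would add to the shortfall. None of this supplies the missing cluster term.

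**Conclusion.** The concern holds and must be fixed. The plan names the school as the randomised unit, then specifies a primary analysis and a power calculation that treat children as independent. The omission is certain from the text. Its size is not, because no ICC is given. For ICCs of 0.02 to 0.10, with 142 per arm and SD 11, adjusted power at the 5% level lies between 84% and 70% for group-only clustering and falls to 54% in the extreme case, against the stated 88%. Unadjusted error exceeds its nominal level at any positive ICC, reaching 8.0-10.7% for a nominal 5% at an ICC of 0.10. An ICC below about 0.014 would make the power loss minor, but the plan does not claim one. The TT versus TT+ loss is secondary.

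**What to change.** - **6.1:** take the FRIENDS–CATS interval from a mixed model with random intercepts for school and school-by-randomisation-list (the unit actually randomised, given the year-5 redraw). Add therapist/group where estimable, and use small-sample degrees of freedom.
- **Fallback, named in advance:** the school-by-list intercept alone, or cluster-robust errors by school with a small-sample correction. With about 1.7 groups per allocation (30/18), the group component may be poorly estimated. The simulation checked the cluster-robust options, not the mixed model.
- **Decision rule:** state it as interval inclusion within ±4.20, at the same confidence level in 6.1 and 6.3.
- **6.3:** restate power with a design effect over a stated ICC range. First reconcile the randomised unit (Abstract and 3.1 against 4.2, 6 and 8.1.1).
- **TT versus TT+:** include a random school or supervisor effect, after reconciling the supervisor counts in 3.2.2 (36-41) and 5.3 (12).

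The cost is rewording, slightly more model code and a lower stated power. No new data or visits are needed.

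### FRIENDS vs CATS: baseline covariates enter only after a balance check with no stated criterion, and the randomisation stratum is in no analysis; one prespecified baseline-adjusted model should replace this.

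*Combined protocol and SAP*

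**What the plan says.** Section 6.1 bases the effectiveness comparison on "differences in symptom severity, impairment, and academic competence (child outcomes) from pre to post between children receiving FRIENDS and children receiving CATS", to be "tested by calculating the 95% confidence limits" and judged against a limit of 4.20. It names no model and no covariate.

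Section 6 notes that schools were the unit of randomisation and that "the potential for imbalances at pre-measurements between students who will be part of FRIENDS or CATS groups are anticipated". The investigators will first see whether student demographics, diagnostic, mental health and academic variables and therapists' "level of experience are balanced in both conditions". Then: "We will account for any differences in the analysis by including such variables as covariates". No test, threshold or variable list follows. Section 6 also keeps open "non-parametric tests such as the Mann-Whitney test for comparing pre/post changes between two independent groups", which is unadjusted.

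Section 8.1.1 stratifies schools by size (above 625 students or not). Later in the same section, the rule for replacing dropped schools gives the stratification variables as size and type. Neither factor appears anywhere in Sections 6 to 6.3.

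One other covariate is planned. Section 4.2 describes an index of instruction time for use in a covariate analysis. It is measured after randomisation and is not tied to the Section 6.1 comparison, so it does not fill the gap.

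**The concern.** Two statisticians following Section 6 could fit different models to the same data, because each must decide what counts as a difference. The conclusion depends on whether limits fall inside ±4.20, so a covariate choice made after seeing balance can move a borderline result across the margin, separately for each outcome. The plan itself expects imbalance, so the rule is likely to be used.

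The second cost is precision. A pre-treatment score of the same outcome is useful whether or not it happens to be balanced. A rule that uses it only when imbalance is seen gives up part of that gain. Omitting the stratum is a different matter: including it matches the analysis to the randomisation, and no precision gain is claimed for it.

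**Working it through.** **Inputs from the documents.** 142 students per arm, limits ±4.20, true difference 0 (Section 6.3); "the standard deviation of the differences in means is assumed to be 11", read here as the SD of the change score; at least 36 schools over three arms (Section 8.1.1), hence 36/3 = 12 per arm.

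**Assumed, because the documents do not give them.** Pre-post correlation r, k = SDpre/SDpost, school ICC, and the balance trigger.

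**The plan's own figure.** SE = 11 × √(2/142) = 1.305. Power of two one-sided tests = 2Φ(4.20/1.305 − 1.645) − 1 = 2Φ(1.572) − 1 = 88.4%; with the t distribution, 88.2%. This matches "achieves 88% power at a 5% significance level when the true difference between the means is 0". On the 95% limits of Section 6.1 (2.5% per side) it is 79.1%, or 78.7% with t. Both are unadjusted and ignore clustering.

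**Baseline adjustment against change score, arms exchangeable at baseline.**

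Var(adjusted)/Var(change) = (1 − r²)/(1 + k² − 2rk). Denominator minus numerator is (k − r)², which is never negative. So the large-sample ratio cannot exceed 1, and equals 1 only when k = r.

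| k | r = 0.5 | r = 0.6 | r = 0.7 |
|---|---|---|---|
| 1.0 | 0.750 | 0.800 | 0.850 |
| 0.9 | 0.824 | 0.877 | 0.927 |
| 0.8 | 0.893 | 0.941 | 0.981 |
| 0.7 | 0.949 | 0.985 | 1.000 |

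**What the balance-triggered rule loses.** Simulation with 20,000 runs per setting, true difference 0, k = 1, 12 schools per arm, the same ICC before and after treatment, a balance t-test ignoring clustering, and year-5 re-randomisation ignored.

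| ICC | r | Trigger | SE change | SE rule | SE always adjusting | Rule/always |
|---|---|---|---|---|---|---|
| 0 | 0.5 | p<0.05 | 1.299 | 1.259 | 1.134 | 1.110 |
| 0 | 0.7 | p<0.05 | 1.313 | 1.288 | 1.210 | 1.064 |
| 0.05 | 0.5 | p<0.05 | 1.631 | 1.528 | 1.413 | 1.081 |
| 0.05 | 0.7 | p<0.05 | 1.636 | 1.575 | 1.505 | 1.047 |
| 0.05 | 0.5 | p<0.20 | 1.631 | 1.459 | 1.413 | 1.033 |
| 0.05 | 0.7 | p<0.20 | 1.636 | 1.534 | 1.505 | 1.019 |

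A repeat of the fourth row gave 1.558/1.492 = 1.044, so the clustered p<0.05 range is about 4-8%. At p<0.50 (r = 0.5, ICC 0.05) a separate run gave 1.443/1.436 = 1.005.

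**The stratum.** In a further simulation (30 groups of 5 per arm, r = 0.5), adding a two-level stratum with no effect on outcome left the SD of the adjusted estimate unchanged (1.087 at ICC 0, 1.209 at ICC 0.05). School size is a school-level factor. With 24 schools in two arms, it takes the degrees of freedom from 24 − 2 = 22 to 21, which costs about 0.2 points of power.

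**If the arms are not exchangeable.** Suppose a stable baseline difference of 0.2 SD, with r = 0.5 and k = 1. The change-score SD is then SD × √(2 − 2 × 0.5) = SD, so the raw SD is 11 and the baseline gap is 0.2 × 11 = 2.2 points at both times. The change score is centred on 0. The adjusted estimate is centred on 2.2 − 0.5 × 2.2 = 1.1, about a quarter of the margin (1.1/4.20 = 0.26). The plan's own rule lies between, at about 0.8 with a p<0.05 trigger and approaching 1.1 with looser triggers.

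**The case against.** The strongest reply is that Section 6 promises to account for any differences, directly after saying that imbalance is expected. Read plainly, that is a low bar, close to routine adjustment, and at p<0.50 almost nothing is lost. This stands as far as precision goes: the loss cannot be stated without assuming a trigger. It does not answer the lack of prespecification, since the text still leaves the criterion and the variables open.

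A reader might infer that the fix raises power from 88% to between 88% and 96%, which is what the variance ratios give at 5% per side. The documents do not support that reading. Those figures ignore clustering, and they compare with a change score that is never adjusted, which is not the plan's rule. On the clustered standard errors above, with 22 degrees of freedom and 5% per side, power is about 60% for the unadjusted change score and 71-78% with adjustment, and these also rest on an assumed ICC.

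A reader might also infer that the plan's rule is biased, or that both analyses are free of bias. Neither follows. With exchangeable arms the rule's mean estimate stayed within 0.02 of zero. But schools are randomised first (Section 8.1.1), and therapists trained in their assigned protocol then screen and refer students (Sections 3.1.1 to 3.1.3 and 4.1), so exchangeability of students is not guaranteed. The 0.2 SD example shows one way in which adjustment shifts the estimate; other assumptions could reverse it.

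Finally, Section 5.2 labels no instrument as the impairment measure, so a model can be written only for outcomes whose measure is defined and collected at baseline.

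**Conclusion.** The point holds as a matter of prespecification, with a precision cost that is real but conditional. The covariate set for each outcome depends on a balance check without a criterion, and no analysis uses the stratum.

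Given exchangeable arms and large samples, always adjusting for the baseline score has 0.75 to 1.00 times the variance of the change score over the assumed ranges, with no gain when r equals SDpre/SDpost. Relative to always adjusting, and with equal variances, 12 schools per arm and ICC 0.05, the plan's rule has a standard error about 4-8% larger at p<0.05, 2-3% at p<0.20 and under 1% at p<0.50.

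The correlation, SD ratio, ICC and trigger are all assumptions. Neither analysis can be declared free of bias, because referral follows randomisation. The change is well worth making, but the plan as written is not invalid without it.

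**What to change.** Replace the balance-triggered rule with one prespecified primary model for each child outcome that has a baseline measure: post-treatment score on arm, baseline score of the same outcome and the randomisation stratification factor(s), with clustering handled at the school level.

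- First reconcile the two statements in Section 8.1.1, size alone against size and type.
- Name any further baseline covariates before data are seen.
- Say whether the Section 4.2 instruction-time index has any role in this comparison; as a post-randomisation variable it should not enter the primary model by default.
- Keep balance tables as description only.
- Report the unadjusted change-score comparison as a sensitivity analysis, and do not state that either analysis is free of bias.

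The cost is SAP wording, about one school-level degree of freedom for size (about 0.2 points of power at 21 rather than 22), more if type is also a factor, and a rule for students without a baseline score. Baseline sessions are already planned (Section 3.2.1), and school size is known at randomisation.
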